SPECIFIC AIMS

Legitimate prescription opioid use during adolescence has been associated with later prescription opioid misuse and substance use disorder symptoms during adulthood.^{1,2} Thus, primary prevention interventions for older adolescents and young adults at the time of prescribing are imperative. With several million opioid prescriptions dispensed to adolescents and young adults each year in the United States,³ providers are uniquely positioned to address and mitigate opioid risks for these vulnerable groups. Indeed, despite a recent plateauing in prescribing rates, opioid-related poisonings, prescription misuse, opioid use disorder and unintentional overdose deaths continue to increase among our youth, suggesting an unrelenting effect of the opioid crisis and an urgent need for action.⁴⁻⁷ Recognizing the urgency for action, state laws have been widely enacted that, among other requirements, mandate informed consent for patients as well as parents of minors who are prescribed opioids. While the intent of such laws is to lessen the impact of the opioid crisis by increasing risk awareness, it is not clear whether such laws are sufficient to enhance risk understanding and mitigate risky behaviors without adversely impacting effective pain management.

We previously demonstrated that opioid risk awareness alone (i.e., knowledge that adverse effects like addiction and excessive sedation can occur) was not related to safer opioid decision-making among parents, whereas higher risk perceptions and analgesic risk avoidance preferences were strongly related.⁸ We have since similarly demonstrated that risk perceptions and analgesic preferences (but not simple risk awareness) were strongly associated with intentions to misuse prescription opioids among a large sample of adolescents and emerging adults.⁹ Finally, desire for pain and other symptom relief remains the most common motive for prescription opioid misuse among adolescents and young adults.^{10,11} Thus, modifiable targets to reduce risky prescription opioid decisions among adolescents/emerging adults include opioid risk perceptions, analgesic risk/benefit preferences and safe pain management knowledge.

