Our current research (R01DA044245) examines the ability of our interactive Scenario Tailored Opioid Messaging Program (STOMP) to shift these modifiable factors in a way that will improve parental opioid decision making and handling while simultaneously ensuring good pain management of their children. This intervention, thus, provides an innovative, balanced approach to address both the primary prevention of opioid-related adverse outcomes and effective pain management. Relevant to this supplement, we will modify STOMP messages and test their impact on opioid risk perceptions and risky decision-making among older adolescents and emerging adults who make most if not all analgesic treatment decisions for themselves.

Supplemental funding via PA-18-591 will enable us to expand the target population of our current project to include older adolescents and emerging adults who are prescribed opioids for an acute pain condition and who are among those at highest risk for misuse. Specifically, funding will allow us to modify our STOMP messages to address the risks of opioid misuse and personal strategies to manage symptoms, and compare the effect of these STOMP messages to routine opioid analgesic consent information. These objectives fall within the scope of our currently funded project, but effectively expand our target enrollment to address the high priority need for primary prevention among youth. Thus, with supplemental funding, we aim to test the following hypothesis:

- 1) Examine whether modified STOMP messages will improve opioid risk understanding, enhance misuse risk perceptions, improve analgesic self-efficacy, and opioid decision-making among older adolescents and emerging adults (ages 15-24) who are prescribed opioids for post-procedure pain management. We hypothesize that older adolescents and young adults who are randomized to the intervention (versus routine opioid information/consent) will exhibit; **(H1)** Greater and sustained understanding of the potential risks of opioid misuse **(H2)** Decreased intentions to medically or non-medically misuse opioids for personal use, or share (divert) personal prescriptions with others.

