Our interactive Scenario Tailored Opioid Message Program (STOMP) intervention was developed based on Fuzzy Trace Theory (FTT) with an aim to change the mental model of risk perceptions and shift preferences in a direction that will reduce risky opioid decisions and enhance best analgesic practices. FTT describes how information (both taught and experienced) is processed to create mental representations ranging from precise data to fuzzy or simple gist representations. Based on this theory and consistent with other neurodevelopmental theories, risky decision-making is a function of the mental representations (verbatim and gist) of the options at hand (e.g., to misuse a prescribed drug or not). In addition to mental representations, reward sensitivity (i.e., the degree to which someone is benefit preferent), time preferences (i.e., desire for immediate reward over later ones), and opportunity (i.e., availability) also factor into risky decision-making. Thus, opioid misuse among adolescents and young adults reflects, to varying degrees, the degree to which the risk-taker desires the positive effect of the drug (reward), the ready availability of the drug, and the risk-taker’s cognitive appraisal of the option to misuse (riskiness). While opioid misuse behavior may initially be goal-directed (i.e., to obtain pain relief or benefit), the slippery slope to addiction is sharper

with opioids than, perhaps, other controlled substances. Thus, primary prevention of misuse behavior must begin with initial exposure to the drug. FTT suggests that the most appropriate and, perhaps, most malleable targets to prevent initial opioid misuse are the mental representations of options, that is, of opioid risk perception and analgesic preferences.⁴¹

INNOVATION

- This extension of our parent project is a natural extension of our innovative, interactive STOMP intervention to a group of older adolescents and young adults who are vulnerable to opioid misuse.
- Our intervention aligns with the National Drug Control Strategy with an overall goal to increase risk recognition, prevent opioid-related adverse events and minimize the capacity for future misuse.
- Our intervention uniquely combines scenario-tailored risk decision exercises with tailored risk messages and evidence based advice. Thus, the information has the ability to enhance target perceptions and improve competency or self-efficacy.

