Our multidisciplinary team brings expertise in acute post-procedure pain management, adolescent substance use behaviors (with a particular emphasis on prescription opioid misuse among adolescents and emerging adults),^{10,11,22,26,28,43} tailored decision-aid technology and evaluation of educational and behavioral interventions in the clinical setting.⁴⁴⁻⁴⁷ Increasing [name] effort from a consulting role to an active co-investigator will bring a more prominent role regarding effective pain management strategies and interpretation of data.

APPROACH

With this supplement, we aim to expand the target population identified in our parent study to include older adolescents and emerging adults (ages 15-24 years) who are beginning to or are solely making analgesic decisions for themselves following a painful procedure.

We will adapt STOMP messages to specifically address the risks of personal misuse of opioid analgesics and the potential risk of sharing prescribed opioids with others. We will modify the analgesic messages that address safe and effective pain management strategies and early opioid weaning.

Using modified surveys but similar procedures as the parent project, we will test the effect of STOMP on the outcomes: opioid risk perceptions, misuse intentions and behaviors, persistent use and left-over disposal intention.

Expanded sample inclusion and justification: We will recruit up to 600 English speaking patients, aged 15-24 of all races who are expected to receive an opioid prescription for acute, short-term postoperative pain following elective ambulatory or short stay (<48 hrs) orthopedic, sports medicine, or other surgical procedures.

Sample exclusions: We will exclude patients who are undergoing emergency procedures, cannot self-report their pain, have a hematologic-oncologic, kidney or liver condition (precluding the usual analgesic prescription patterns), or who have been recently treated for chronic pain. We will exclude subjects with significant mental health history that includes diagnoses with treatment for severe depression, bipolar disorder, psychoses, suicidal ideation.

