Protection against risk (see Parent Protection of Human Subjects for more detail): Our opioid messages are developed with the guidance of pediatric pain and risk communications experts. The intervention poses no more than minimal risk to adolescents or young adults but may instead, offer potential benefit in terms of risk reduction, self-efficacy and pain management competency.

We will minimize the risk for breach of confidentiality of all participants by training of study team members, use of electronic and physical security measures for data capture and storage, and by employing a Certificate of Confidentiality (automatic for NIH funded studies). Unique study identifiers (ID) for each subject will permit linkage between surveys and follow-up data while maintaining the privacy of every participant. ID links between subjects and their data will be kept separately in an encrypted file. Data will only be stored on fire-walled databases which will limit access only to those assigned appropriate permissions.

Routine management will not be altered and we will exclude those who cannot, by nature of their underlying condition be safely prescribed the usual combination of opioids and non-opioids for postoperative pain. We will record all adverse events and will review non-serious AEs

quarterly and serious AEs as they are learned to determine the relationship to study participation and actions needed, if any (see DSMP).

Data and safety monitoring plan (DSMP): Our study specific DSMP provides details of how we will collect, review, evaluate and manage adverse events that may happen as part of routine care or study participation.

Group assignment (same as parent study): Patients will be randomly assigned a priori by computer generated randomization to either the Control Group (i.e., Routine provider written/verbal analgesic instruction) or one of two Intervention Groups: STOMP written (prose) feedback (i.e., Routine provider information plus the STOMP written feedback or our enhanced STOMP Video feedback (i.e., Routine provider information plus STOMP Video feedback).

Outcomes

Aim 1) Opioid risk perceptions, misuse risk perceptions, intentions to medically misuse, non-medically misuse or divert left-over opioids

Aim 2) Persistent opioid use after surgery, left-over opioid retention

Measurements (only modifications from parent grant are described)

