- **Analgesic adherence:** Participants will record postoperative analgesics administered, self-reported pain scores (i.e. 0-10 Numeric Rating Scale), and adverse effects the follow-up surveys. Opioids will be converted to oral morphine equivalents, and opioid and non-opioid consumption will be reported as total mg/kg given. Adherence will be reported as the percentage used of the total opioid and non-opioid doses prescribed. The number of left-over doses of opioids will be calculated at discontinuation (amount dispensed minus amount used). We will assess intention to keep left-overs and reasoning at follow-up.
- **Pain interference:** The PROMIS Adult Pain Interference Short Form will also be used to measure how much pain is interfering with participants' activities at 1 and 2 weeks.^{48,49}
- **Adverse side effects:** Participants will document all analgesic-related side effects using the follow-up surveys.⁷ We will also review the clinic notes (6 months) for surgical and analgesic-related calls, return visits to the clinic or hospital, and analgesic refill orders, and persistent pain documentation.

Measurements of Contributing Factors

- **Key biologic and other characteristics of the participant:** Participants will record their demographics including sex and race and ethnicity.
- **Substance Use:** We will use the ASSIST measure for adults as a gross measure of risk factors for substance use disorder.⁵⁰
- **Pain history and opioid familiarity:** History of participant pain, opioid and non-opioid use will be assessed with simple categorical items.^{8,46}
- **Pain relief preference (PR-Pref):** This instrument assesses the participant's desire to provide pain relief relative to their desire to minimize ADE risks. The instrument includes 7 risk–benefit items^{7,8,46} similar to those used to assess the importance patients place on chronic medication benefits versus their concern for adverse effects.¹⁴⁵⁻¹⁴⁷ Agreement with each statement is ranked on a 5 point Likert scale from strongly disagree (-2) to strongly agree (+2), to yield a total score ranging from -12 to +12, where lower numbers indicate a preference for risk avoidance, higher numbers pain relief, and the middle range, indifference or ambivalence.^{145,147} We previously have demonstrated the instrument's internal consistency, construct and predictive validity (higher scores predict parental opioid administration).⁴⁶

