Our sample size is based on our recent findings that 26% of adolescents/young adults indicated a willingness to misuse a prescribed opioid for pain management. We need 426 participants (142/group) to detect a clinically important effect of the STOMP intervention on misuse intention (i.e., decrease to 13%; 95% confidence and 80% power). This sample will be more than sufficient to detect an expected mean difference in opioid misuse risk perception between either intervention group and the control (MD 0.56, SD 1.21; sample needed = 122) and to test for a modest effect of the interventions in a factorial design (estimated eta squared 0.14; sample needed = 147). To allow for 30% loss to follow-up and to account for missing data, we will recruit up to 600 participants.

Table 1. Sequence of study assessments

Measures	Time 0 Baseline (preop)	Time 0.1 (Immediately Post-Session)	Time 1 (7 days)	Time 2 (14 days)	Time 3 (1 month)	Time 4 (3 months)
Demographics	x					
Pain, Analgesic and Misuse History	x					
Pain relief Preference	x			x		
Opioid knowledge/ risk perceptions	x	x		x	x	x
Opioid misuse risk perceptions	x	x		x	x	x
Scenario (situational) decision-making	x			x	x	x
Analgesic self-efficacy	x	x				
Pain interference			x	x	x	x
Opioid left-over disposal				x	x	x

Analgesic use and ADEs			x	x	x	x
Perioperative data	x					
Analgesic refill data				x		

DATA ANALYSES

Generalized estimating equations (GEE) will be used to model both continuous (i.e., negative binomial and Gaussian) and binary outcomes (i.e., binomial) for each aim.^{151,152} All models will include both time-varying measures (e.g., opioid risk perceptions) and time-invariant covariates (e.g., sex, race, etc.) and will use either an independent or exchangeable correlation structure to correct for within subject correlations. Analyses will use Stata's (STATA/SE v.13; STATA Corp., College Station, TX) 'xtgee' option as appropriate. All hypotheses per our conceptual model (Figure 3) will be tested at the 0.05 alpha level. Standardized coefficients and adjusted odds ratios will be computed to determine the relative effect size for each of the key independent variables.

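### Analgesic preference, one of STOMP's three stated targets, has no prespecified between-arm test, and the covariate rule, read literally, admits post-randomisation STOMP targets into the misuse-intention model

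*Combined protocol and SAP*

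**What the plan says.** **Target.** The Specific Aims state that "modifiable targets to reduce risky prescription opioid decisions among adolescents/emerging adults include opioid risk perceptions, analgesic risk/benefit preferences and safe pain management knowledge". The Scientific Premise says STOMP was developed "with an aim to change the mental model of risk perceptions and shift preferences in a direction that will reduce risky opioid decisions". The background on youth knowledge and perceptions reports that a stronger preference for pain relief was strongly associated with intention to misuse.

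**Measurement.** PR-Pref is described under Measurements of Contributing Factors, beside demographics, substance use, pain history and surgical factors: "This instrument assesses the participant's desire to provide pain relief relative to their desire to minimize ADE risks". Table 1 marks it at Time 0 and Time 2 (14 days) only.

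**Outcomes.** The Approach lists "opioid risk perceptions, misuse intentions and behaviors, persistent use and left-over disposal intention". The Outcomes section gives "Aim 1) Opioid risk perceptions, misuse risk perceptions, intentions to medically misuse, non-medically misuse or divert left-over opioids" and, for Aim 2, persistent use and left-over retention. The Aim 1 analysis paragraph models risk seriousness perception and situational decisions. Preference is in none of these.

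**Models.** Data Analyses says: "All models will include both time-varying measures (e.g., opioid risk perceptions) and time-invariant covariates (e.g., sex, race, etc". The section does not say which time-varying measures enter which model, or whether only their baseline values are used.

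**The concern.** Two things follow.

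First, preference is treated differently from its companion target. Risk perception is a target, an outcome and the subject of a planned group-by-time contrast. Preference is a target measured before and after STOMP, with no planned contrast. If the trial shows fewer misuse intentions, the plan has no prespecified way to say whether preferences moved.

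Second, the covariate rule names as its example a variable that STOMP is meant to change and that is itself an Aim 1 outcome. Conditioning on a post-randomisation variable that lies between STOMP and misuse intention no longer estimates the total effect of being assigned to STOMP. It estimates what is left after that path is blocked, and even that reading needs assumptions that randomisation does not supply. H2 is a claim about the total effect, and the sample size was set for it.

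**Working it through.** **1. The plan's own figure.** Sample Size Determination gives 26% v 13%, 80% power and 142 per group. With two-sided 0.05 (sidedness assumed) and unpooled variances:

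n = (1.960 + 0.842)² × (0.26×0.74 + 0.13×0.87) / 0.13² = 141.9, so 142.

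The figure reproduces, and this point does not affect it. The planned effect on the log-odds scale is ln[(0.13/0.87)/(0.26/0.74)] = −0.855, an odds ratio of 0.425.

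**2. Could the collected data test preference?** Detectable standardised difference at 80% power = 2.80 × √(1/n₁ + 1/n₂):

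- One STOMP arm v control, 142 v 142: 0.33 SD.
- Both STOMP arms v control, 284 v 142: 0.29 SD.
- With adjustment for Time 0 PR-Pref at an assumed correlation of 0.6, multiply by √(1 − 0.36) = 0.8: 0.27 and 0.23 SD.

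The sample is adequate for moderate shifts. What is missing is a planned comparison.

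**3. What adjusting for 14-day PR-Pref could remove.** The documents give no PR-Pref SD, no expected shift and no odds ratio per SD. Assumptions: PR-Pref is normal with SD 1 in each arm, STOMP lowers it by d, and misuse intention follows a logistic model in arm and PR-Pref. The marginal rates are held at 26% and 13%, and the model is solved for the adjusted STOMP coefficient.

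| Shift d (SD) | OR per SD | Adjusted log OR | Adjusted OR | Shrinkage from −0.855 |
|---|---|---|---|---|
| 0.20 | 1.50 | −0.795 | 0.451 | 7% |
| 0.35 | 1.75 | −0.700 | 0.497 | 18% |
| 0.50 | 2.00 | −0.571 | 0.565 | 33% |

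The shortcut d × ln(OR per SD) / 0.855 gives 9.5%, 23% and 40.5%. It is too high here because it divides a path on the conditional scale by a marginal log odds ratio, and odds ratios are not collapsible.

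**4. When it could apply.** In Table 1, scenario decisions follow baseline at 14 days, 1 month and 3 months. PR-Pref has a follow-up value only at 14 days, so the shrinkage applies directly at that visit. Risk perceptions are measured at all three of those follow-ups, so the same rule could affect every one of them.

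**5. Scoring.** PR-Pref has 7 items scored −2 to +2, so totals run from 7 × (−2) = −14 to 7 × 2 = +14. The measurement section states −12 to +12, which would fit 6 items.

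**The case against.** The best defence is that the omission matches the stated hypotheses. Aim 1, H1 and H2 concern risk understanding, misuse risk perceptions, self-efficacy, decisions and intentions. The mediation hypothesis in Aim 2 runs through risk perceptions only. Preference is one of three targets, and a trial need not test every path in its theory. This stands as far as it goes: leaving preference out does not contradict the hypotheses. It does leave a stated target untested when the data are being collected anyway.

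On the models, no section names PR-Pref as a covariate. The Aim 1 paragraph mentions only group, time and their interaction. The covariate sentence cannot be meant literally for all models, since its example is itself an outcome. Using Time 0 PR-Pref alone would be harmless, and the 14-day score would be missing at two of the three decision follow-ups unless carried forward, which is nowhere proposed. All of this stands, and it makes over-adjustment a risk left open by the wording, not a stated plan. The clearest documented case is risk perceptions. PR-Pref follows from the same sentence.

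Finally, the measurement section describes only changes from the parent grant, and the hypotheses refer to a conceptual model in Figure 3. Neither is in the text. The Specific Aims say the parent project examines STOMP's ability "to shift these modifiable factors in a way that will improve parental opioid decision making", so a preference test may be planned there.

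A reader might infer that the trial cannot show whether STOMP shifts preference. The documents do not support that: Table 1 schedules PR-Pref at both times without distinguishing arms, so the comparison can be run.

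**Conclusion.** The point holds in a limited form. A stated STOMP target is measured before and after the intervention with no between-arm comparison prespecified in these documents, so a finding on it would be post hoc and limited to 14 days. Separately, the covariate rule as written admits post-randomisation values of STOMP targets into the misuse-intention model.

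The size of the second problem is not known from the documents. The 7% to 33% shrinkage rests entirely on the assumed shift and odds ratio, and applies directly only at 14 days. It would be wrong to infer that the plan will adjust away that share of the H2 effect. It shows what the current wording permits. The change is worth making because it costs little and protects the trial's main contrast.

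**What to change.** - **Data Analyses:** state that the models for the total effect of STOMP adjust only for baseline (Time 0) values. Post-randomisation values of STOMP targets (PR-Pref and risk perceptions) enter only as outcomes or in a separate, named mediation analysis.
- **Outcomes:** list 14-day PR-Pref as a secondary Aim 1 outcome, STOMP v control, adjusted for Time 0 PR-Pref. If Figure 3 or the parent grant already plans this test, bring the statement into the written analysis.
- **Measurements of Contributing Factors:** before PR-Pref is used as an outcome, reconcile the number of items with the stated score range.

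The cost is revised wording and one extra model on data already collected, with no new assessments or participants. The downside is one more secondary test.

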- **Surgical factors:** The procedure, prior injury, duration of surgery, all perioperative analgesics given and details of participant's prescription and analgesic instructions will be recorded from the medical record.

Study Procedures (SEE TABLE 1 BELOW)

Group assignment: Participants will be randomly assigned a priori by computer generated randomization to one of the three groups: the Control Group (i.e., Routine provider

pen/verbal analgesic instruction), the STOMP written feedback (intervention) Group: (i.e., Routine provider information plus the STOMP written feedback) or the enhanced STOMP Video Feedback (intervention) Group (i.e., Routine provider information plus the STOMP Video feedback).

All baseline and follow-up surveys are completed by the subjects using a Qualtrics survey link via their own smartphone or computer (or our iPad if completed in person) to ensure completeness and privacy. Subjects will enter only an assigned, unique ID number with no other identifying information. STOMP (either written or video groups) will be provided together with each decision exercise (built into the survey itself). The electronic survey includes appropriate logic and prompts to minimize the potential for missing items.

Subjects will be texted/emailed survey links on day 0 (day before or on surgery), day 7, day 14, 1 & 3 months after discharge. Table 1 depicts the study assessments completed at each timepoint. These will be automatically scheduled via our umich gmail system. On each of the survey days, we will also send a text SMS reminder to participants (automated using the same process as our parent study). Subjects can opt to complete surveys via email link (Qualtrics) or via paper/pen (returned via mail). No more than 1 additional text reminder for each will be sent to subjects who have not completed their follow-up surveys.

Sample Size Determination

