Confidentiality: We will minimize the risk of confidentiality breach by assuring privacy during our recruiting/consenting procedures, through the use of surveys and paperwork containing no identifiers (only assigned study ID links), and the maintenance of linkage lists, databases, etc. on institutional computers (protected by the use of secure login procedures). Consent forms will be stored separately from datasheets, to avoid the additional possibility of linking materials. A Certificate of Confidentiality has been granted by NIH to further protect study participants from breach of confidentiality.

Adverse Events: To ensure that our intervention poses no risk to safe or effective pain management, we will monitor all adverse events related to routine care (e.g., opioid-related drug effects, surgical events, and unplanned hospitalization) per our DSMP to determine whether either group (intervention or control) has been placed at greater risk for these events. Serious and non-serious events will be reviewed and reported as outlined in the DSMP.

Potential Benefits of the Research to Human Subjects: Since the nature of this study is to enhance and motivate safe use and management of opioid analgesics, those who take part and who are randomized to the intervention(s) might benefit from this knowledge and skill building program. Of note, our pilot data also showed that being in the Control group enhanced awareness of opioid-related ADEs (though did not have a significant effect on hypothetical decisions). Additionally, this study has the potential to yield information and interventions that may benefit participants in the future. This potential benefit of our ability to improve participant knowledge and decision-making around opioid risks far outweighs the minimal risks posed by study participation.

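### PROMIS Pain Interference is scheduled at 1 and 2 weeks in the measurement text but out to 3 months in Table 1, and neither schedule has a pre-operative score

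*Combined protocol and SAP*

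**What the plan says.** Two current parts of the document give different timings for the same instrument.

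- Measurements, Pain interference: the PROMIS adult short form records how far pain limits "activities at 1 and 2 weeks".
- Table 1: the row reads "Pain interference x x x x", with marks under 7 days, 14 days, 1 month and 3 months. The pre-operative and immediate post-session columns are blank.

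Study Procedures says that "Table 1 depicts the study assessments completed at each timepoint", and sends survey links on "day 0 (day before or on surgery), day 7, day 14, 1 & 3 months after discharge". A survey therefore goes out at every point in dispute, and also before surgery.

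Other pain information is planned. Under Analgesic adherence, participants give 0-10 numeric pain scores in the follow-up surveys. Under Adverse side effects, clinic notes are reviewed (6 months) for refill orders and documented persistent pain, among other items. Pain history is taken at baseline with categorical items.

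The Aim 2 outcomes are "Persistent opioid use after surgery, left-over opioid retention". Table 1 collects analgesic use at all four follow-up waves, including 1 and 3 months.

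**The concern.** The two schedules agree on the first two weeks and part at 1 and 3 months, when opioid use is recorded for Aim 2. The protocol's rationale is that pain relief is the commonest motive for misuse, so a functional pain measure taken at the same survey helps the reader interpret continued use. Survey links are scheduled automatically. A team that programs them from the measurement text would omit the form at the late waves, and those data could not be recovered.

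The second gap is common to both schedules. Patients come for elective orthopedic, sports medicine or other surgery, and prior injury is recorded as a surgical factor, so pain interference before surgery plausibly differs between patients. With no pre-operative score on the same scale, whatever part of that difference the recorded covariates do not explain stays in the residual error of each pain-interference comparison. The last paragraph of the Significance section expects the intervention to improve pain outcomes as well as decisions, so the precision of that comparison is of some interest.

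**Working it through.** **1. The schedules side by side**

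| Survey | Measurements text | Table 1, pain interference | Table 1, analgesic use and ADEs |
|---|---|---|---|
| Time 0 (pre-op) | no | no | no |
| 7 days | yes | yes | yes |
| 14 days | yes | yes | yes |
| 1 month | no | yes | yes |
| 3 months | no | yes | yes |

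The text omits 2 of the 4 waves in Table 1, and both are the later ones. At those two waves analgesic use is collected under Table 1.

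**2. What remains if the text is followed**

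The 0-10 pain scores and the note review remain. The pain scores have no row in Table 1. Their timing is inferred from the statement that they are recorded in the follow-up surveys, together with the analgesic-use row, which runs from 7 days to 3 months. They measure intensity, not interference with activities.

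**3. The plan's own figure, used below as an input**

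The plan gives no sample size or precision figure for pain interference. Its 142 per group comes from Sample Size Determination (26% against 13%, 80% power, two-sided 0.05 taken from the stated 95% confidence). With unpooled variance:

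n = (1.960 + 0.842)² × (0.26 × 0.74 + 0.13 × 0.87) / 0.13² = 7.849 × 0.3055 / 0.0169 = 141.9, so 142 per group. The figure reproduces.

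**4. Cost of having no pre-operative score**

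Adjusting for a baseline with correlation r to follow-up multiplies the variance of the arm contrast by 1 − r². The documents give no r, so the values here are assumptions.

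Without adjustment, the detectable difference for two arms of 142 at 80% power is 2.802 × √(2/142) = 0.33 SD. With adjustment it is that value times √(1 − r²).

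| Assumed r | Variance reduction, r² | Detectable difference (SD) |
|---|---|---|
| no baseline | 0% | 0.33 |
| 0.3 | 9% | 0.33 × √0.91 = 0.32 |
| 0.5 | 25% | 0.33 × √0.75 = 0.29 |
| 0.6 | 36% | 0.33 × √0.64 = 0.27 |

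These gains are relative to no baseline adjustment at all. Where pain history, procedure or prior injury already explain part of the same variation, the added gain is smaller.

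**5. Bias**

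Allocation is by computer-generated randomisation, so the absence of a baseline score does not in itself bias the difference between arms. The loss is in precision and in description.

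**The case against.** The best defence is that Table 1 is the schedule. Study Procedures points to it twice, once in its heading, so the phrase in the measurement text may simply be out of date. On that reading, pain interference is collected at 1 and 3 months in the same columns as analgesic use, and nothing is lost. This is the more natural reading and it stands. It does not close the point, because the document states no order of precedence. The Measurements section also says that it describes only changes from the parent grant, which makes its timing look specific to this supplement.

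A reader might go further and infer that persistent opioid use, and the assurance about pain control, have no pain data behind them. The documents do not support that. Even under the shorter schedule the pain scores and the note review remain. The sentence beginning "To ensure that our intervention poses no risk to safe or effective pain management" goes on to adverse-event monitoring. It is not a test of pain interference, and pain interference is not listed as an outcome of either aim.

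On the baseline score, the defence is that this is an option, not a defect. Randomisation protects the comparison, patients recently treated for chronic pain are excluded, several related covariates are recorded, and the gain in detectable difference is modest. Most of this stands. The document gives no figure for how much pre-operative interference varies, and the exclusion narrows that variation without removing it. A baseline measure might also exist in the parent protocol, which is not available here; what can be said is that this document neither describes nor schedules one.

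**Conclusion.** The contradiction is firm and should be resolved before the surveys are built or locked. Its size is two of four waves, both at times when opioid use for Aim 2 is recorded. The loss is conditional: it happens only if the measurement text is followed in place of Table 1.

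The missing Time 0 score is a smaller matter of efficiency. Its size rests wholly on the assumed correlation: about 9% to 36% of the variance for r from 0.3 to 0.6, which takes the detectable difference from 0.33 SD to between 0.32 and 0.27 SD with 142 per arm. It should not be read as a source of bias in the arm contrast.

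**What to change.** 1. Change the timing in the Measurements text to match Table 1: 7 days, 14 days, 1 month and 3 months.
2. Add the same short form to the Time 0 survey and mark that column in Table 1. Place it before any STOMP content, since the STOMP feedback is delivered inside the survey with the decision exercises.
3. State in Data Analyses that the pain-interference comparison is adjusted for the Time 0 score. That section now has a paragraph for Aim 1 only and does not mention pain interference.
4. Report opioid use at 1 and 3 months alongside pain interference from the same survey.

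The cost is a wording change, one mark in Table 1, a sentence on analysis and one short form in an e-survey that already exists. The downside is a slightly longer baseline survey. No additional patients or contacts are needed.
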